2.1.4.2 Deaths

The deaths observation period are per the observation periods defined above.

2.1.4.3 Laboratory safety variables

Clinical laboratory data consists of blood analysis, including hematology, clinical chemistry, and urinalysis. Clinical laboratory values will be converted to standard international units and analyzed in standard international units; international units will be used in all listings and tables. Baseline values for clinical laboratory variables will be the original baseline from the parent study.

Blood samples for clinical laboratories will be collected at Visit1, Visit 4 (Week 4), Visit 8 (Week 12), Visit 11 (Week 24), Visit 13 (Week 48; if applicable), Visit 15 (Week 72; if applicable), 17 (End-of-Treatment), 18 (End-of-Study) and/or early termination, unless otherwise specified. The laboratory parameters will be classified as follows:

- Hematology:
 - **Red blood cells and platelets and coagulation:** hemoglobin, hematocrit, platelet count and total red blood cell count.
 - White blood cells: total white blood cell count, with five-part differential count (neutrophils, lymphocytes, monocytes, basophils, eosinophils).
- Clinical chemistry
 - Metabolism: glucose, total cholesterol, total protein, creatine phosphokinase.
 - Electrolytes: sodium, potassium, chloride, bicarbonate
 - Renal function: creatinine, creatinine clearance, blood urea nitrogen, uric acid
 - Liver function: alanine aminotransferase, aspartate aminotransferase, alkaline phosphatase, total bilirubin, albumin
 - **Pregnancy test**: A serum pregnancy test (β-human chorionic gonadotrophin) performed at screening (Visit 1) in women of childbearing potential will be applicable to patients coming from DRI12544.
 - **Hepatitis screen**: A hepatitis screen (hepatitis B surface antigen [HBsAg], Hepatitis B IgM core antibody [HBcAb-IgM], hepatitis C antibodies [HC Ab]) will be performed at Visit 1.
 - **HIV screen**: HIV screen (Anti-HIV-1 and HIV-2 antibodies) will be performed at Visit 1.
 - **Antibody**: anti-nuclear antibody (ANA) at Visit 1. Note: Anti-double-strand DNA antibody will be tested if ANA is positive (≥1:160 titer).
- Serum immunoglobulin quantitative immunoassays (IEP) (IgG, IgG subclasses 1-4 subtypes, IgM, and IgA). The collection for serum immunoglobulin will be stopped after the approval of protocol amendment 4. The analyses for IgG, IgG subclasses 1-4 subtypes, IgM, and IgA in LTS12551 study will be restricted to the patients from DRI12544 study and performed to the data observed up to the end of collection.

Urine samples will be collected as follows:

• Urinalysis - Quantitative analyses: pH, glucose, ketones, leukocyte esterase, blood, protein, nitrate, urobilinogen and bilirubin (by dipstick). If any parameter on the dipstick is abnormal, a urine sample should be sent to the central laboratory for testing. If positive for proteins, microscopic analysis is performed by central laboratory. Testing is performed at Visit 1, Visit 8 (Week 12), Visit 11 (Week 24), Visit 13 (Week 48; if applicable), Visit 15 (Week 72; if applicable), Visit 16 (Week 84; if applicable), Visit 17 (End-of-Treatment) and Visit 18 (End-of-Study).

• **Pregnancy test**: Qualifying pregnancy test for patients coming from EFC13579, EFC13691 and PDY14192 studies will be the urine pregnancy test performed at the combined EOT/V1/V2 visit. The urine pregnancy test will be performed at visit 2 (Day 1) and every scheduled visit from Visit 4 (Week 4) to Visit 18 (End-of-Study).

Technical formulas are described in Section 2.5.1.

2.1.4.4 Vital signs variables

Vital signs, including blood pressure (mmHg), heart rate (beats per minute), respiratory rate (breaths per minute), body temperature (degrees Celsius) and body weight (kg) will be measured at every scheduled visit. Height (cm) will be measured at Visit 1 only. Vital signs will be measured in the sitting position using the same arm at each visit, and will be measured prior to receiving investigational product at the study visits. Baseline values for vital signs will be the original baseline from the parent studies.

2.1.4.5 Electrocardiogram variables

ECG results will be from an independent central lab. Baseline values for ECG will be the original baseline from the parent study.

One recording of a standard 12-lead ECG will be performed at Visit 1, Visit 11 (Week 24), Visit 13 (Week 48; if applicable), Visit 17 (End-of-Treatment) and Visit 18 (End-of-Study). A minimum of 3 complexes in an appropriate lead (lead II) will be averaged to determine the PR-interval, QT/QTcF/QTcB interval, QRS-complex and heart rate will be measured for each ECG. At the post-enrollment visits, ECGs will be performed prior to investigational product administration. All ECGs will be performed with the subject in a reclined position.

2.1.5 Pharmacokinetic variables

Blood samples of serum functional dupilumab are collected at Visit 1, Visit 4 (Week 4), Visit 8 (Week 12), Visit 11 (Week 24), Visit 13 (Week 48; if applicable), Visit 15 (Week 72; if applicable), Visit 17 (End-of-Treatment), Visit 18 (End-of-Study) and/or early termination, and before the IMP administration at corresponding scheduled visits that are specified in the protocol. The pre-dose serum dupilumab concentration will be collected at the scheduled visits in LTS12551 study. The baseline values for PK variables are the original baselines from the parent studies.

2.1.6 Anti-drug antibody (ADA) variables

Samples for anti-drug antibodies (ADAs) are collected at various time points throughout the study. ADA samples collected at Visit 1, Visit 8 (Week 12), Visit 11 (Week 24), Visit 13 (Week 48; if applicable), Visit 15 (Week 72; if applicable), Visit 17 (End-of-Treatment), Visit 18 (End-of-Study) and/or early termination will be analyzed for ADA. The baseline used to define ADA variables refers to the baseline value in the parent study. In response to AE's of special interest like anaphylaxis or hypersensitivity additional ADA samples closer to the event may be analyzed, based on the judgment of the medical investigator and/or medical monitor.

The ADA variables include ADA status (positive or negative) and titer as follows:

• Number of patients with pre-existing immunoreactivity

Pre-existing immunoreactivity is defined as either an ADA positive response in the assay at baseline of the parent study with all post first dose ADA results negative in the current study, or an ADA positive response at baseline of the parent study with all post first dose ADA results in the current study less than 4-fold of the baseline titer levels of the parent study.

• Number of patients with treatment-emergent response in the ADA assay

Treatment-emergent response is defined as a positive response in the ADA assay post first dose in the current study, when baseline status in the parent study is negative or missing. The treatment-emergent response is further characterized as:

- Persistent response defined as a treatment-emergent ADA positive response with two or more consecutive ADA positive sampling time points separated by greater than 12-week period (greater than 84 days), with no ADA negative sample in between.
- Indeterminate response defined as a treatment-emergent response with only the last collected sample positive in the ADA assay.
- Transient response defined as a treatment-emergent ADA positive response that is not considered persistent or indeterminate.
- Number of patients with treatment-boosted response in the ADA assay

Treatment-boosted response is defined as a positive response in the ADA assay post first dose in the current study that is greater than or equal to 4-fold of the baseline titer levels of the parent studies, when baseline status of the parent studies are positive.

- Titer values (titer value category)
 - Low (titer <1,000)
 - Moderate $(1,000 \le \text{titer} \le 10,000)$
 - High (titer >10,000).
- ADA positive samples will be further characterized for the presence of neutralizing antibody (NAb) response

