11.4.4.2 Anti-drug antibodies analysis

The ADA analyses will be performed on the ADA population. The baseline value of each applicable ADA variable is the original baseline from the parent studies.

The incidence of positivity in the ADA assay will be assessed as absolute occurrence (n) and percent of patients (%). Listing of ADA titer levels will be provided for patients positive in the ADA assay. Samples that are positive in the ADA assay will be further characterized for the presence of anti-dupilumab neutralizing antibodies, if applicable. Assessment of the potential impact of ADA on safety, efficacy, and PK may be provided. The ADA analyses will be detailed in SAP.

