EFC13579: A phase 3, randomized, double blind, placebo-controlled, parallel group study to evaluate the efficacy and safety of dupilumab SC for 52 weeks in patients with persistent asthma. Patients were randomized in ratio of 2:2:1:1 into the following regimens, dupilumab 200 mg q2w, dupilumab 300 mg q2w, placebo matching 200mg q2w and placebo matching 300 mg q2w. In the treatment period, patients are allowed to administer a stable background therapy of medium to high dose of inhaled corticosteroid (ICS) in combination with a second controller medication (for example, long-acting beta agonist [LABA], leukotriene receptor antagonist [LTRA], theophylline, and etc.), and potentially plus a third controller medication. There were in total 1902 patients randomized for EFC13579.

EFC13691: A phase 3, randomized, double-blind, placebo-controlled study to evaluate the efficacy and safety of dupilumab 300 mg q2w SC for 24 weeks in patients with severe oral corticosteroid dependent asthma. Patients are randomized in a ratio of 1:1 to dupilumab 300 mg q2w and matching placebo, which will be given on top of standard of care and of oral corticosteroids. During the course of the study, the oral corticosteroid (OCS) [prednisone/prednisolone] doses will be adjusted to the dose required for the maintenance of asthma control. In the screening period, patients experience an OCS dose optimization process. In the treatment period, patients continue with the optimized OCS doses in the first 4 weeks, then have the OCS dose down-titrated till Week 20, and at last maintain on the Week 20 OCS dose for the rest 4 weeks. In the meantime, patients are also allowed to be on a stable dose of high dose ICS with a second controller medication (LABA, LTRA, theophylline, etc), and potentially plus a third controller medication per requested by patients. There were in total 210 patients randomized for EFC13691.

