2.3.2 Safety population

The safety population is defined as the patients who have actually received at least 1 dose or part of a dose of the IMP in LTS12551.

Enrolled patients for whom it is unclear whether they took the IMP or not will be included in the safety population as enrolled.

The treatment category "Placebo/Dupilumab" is defined as the patients who have been in the actual placebo arms of the parent studies and exposed to Dupilumab in LTS12551. The treatment category "Dupilumab/Dupilumab" is defined as the patients who have been in the actual Dupilumab arms of the parent studies and exposed to Dupilumab in LTS12551.

For the OCS dependent patients, results of each planned analysis will be presented by "Placebo/Dupilumab", "Dupilumab/Dupilumab" and "All".

For the non-OCS dependent patients, results of each planned analysis will be presented by the parent study and "All", and further by "Placebo/Dupilumab" and "Dupilumab/Dupilumab" within each parent study.

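### For Placebo/Dupilumab patients, ADA response is classified against a parent-study sample taken nominally 12 to 52 weeks before first dupilumab, which can misclassify in both directions

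*SAP*

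**What the plan says.** SAP 2.1.6 sets one ADA baseline for all patients: "The baseline used to define ADA variables refers to the baseline value in the parent study". SAP 2.4.7 repeats it, and Protocol 11.4.4.2 agrees: "The baseline value of each applicable ADA variable is the original baseline from the parent studies".

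Treatment-emergent response has two conditions. The first is "a positive response in the ADA assay post first dose in the current study"; the second applies "when baseline status in the parent study is negative or missing". The pre-existing and treatment-boosted classes use the parent result too: both need a positive parent baseline, and a 4-fold titre ratio to that baseline separates them.

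SAP 2.3.2 defines Placebo/Dupilumab as "patients who have been in the actual placebo arms of the parent studies and exposed to Dupilumab in LTS12551". Their first dupilumab dose is therefore the first LTS12551 dose. No separate ADA rule is given for them.

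A sample from before that dose exists. Protocol 10.1.1.1 and 10.1.2.1 list serum for ADA before dosing at the combined V1/V2 visit. SAP 2.1.6 includes Visit 1 among the analyzed ADA visits, and SAP Table 7 gives ADA a Week 0 window. SAP 2.4.7.2 would show this result in the by-visit ADA status. None of the three class definitions refers to it.

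**The concern.** The rule combines two reference points: the post-dose result is anchored in LTS12551, and the baseline in the parent study. For Dupilumab/Dupilumab patients the parent baseline is the last drug-naive sample, so it is the right comparator. For Placebo/Dupilumab patients it is not, because a drug-free interval of up to a year, or more for late DRI12544 entrants, separates it from the first dupilumab dose. Any change in ADA status during that interval is read as if it followed dupilumab.

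The clause on missing results is the hardest to defend. A patient with no parent result is handled as negative even if a positive pre-dose result is on file.

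The SAP takes more care elsewhere. Sections 2.4.5.3 to 2.4.5.5 tabulate laboratory, vital-sign and ECG abnormalities by status at parent baseline and again at Week 0. Section 2.4.6.1 has a Week 0 concentration rule for parent-placebo patients.

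ADA is a stated secondary objective. Placebo/Dupilumab is the category whose whole dupilumab exposure lies inside this study, and it is reported separately, so errors there are not diluted. Treatment-emergent status also decides who is subtyped as persistent, indeterminate or transient.

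**Working it through.** **1. Plan's own figure.** Parent sizes from SAP 1.1: 776 + 1902 + 210 + 42 = 2930, which reproduces the maximum in SAP 1.3.

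**2. Patients exposed to the rule and the gap.** Placebo share comes from the allocation ratios in SAP 1.1 (for EFC13579: "Patients were randomized in ratio of 2:2:1:1 into the following regimens"). Gap = nominal time from parent baseline to first LTS12551 dose.

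| Parent study | Placebo patients | Gap (weeks) |
|---|---|---|
| DRI12544 | 776 × 1/5 = 155.2 | 24 + 16 = 40, plus 0 to 3 screening; later entry was allowed |
| EFC13579 | 1902 × 2/6 = 634 | 52 |
| EFC13691 | 210 × 1/2 = 105 | 24 |
| PDY14192 | 42 × 1/2 = 21 | 12 |
| Total | about 915 | |

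915/2930 = 31%. Of these, 634/915 = 69% have the 52-week gap. This is a ceiling, because it assumes every randomized placebo patient rolls over. The protocol synopsis expects approximately 2206 patients. If the placebo share stays at 31% (assumed), 2206 × 915.2/2930 = 689.

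**3. Classification under each baseline.** Only the patterns where the two baselines disagree are listed.

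| Parent baseline | Pre-dose LTS12551 | Post-dose | SAP rule | Pre-dose baseline |
|---|---|---|---|---|
| negative or missing | positive | positive, <4-fold | treatment-emergent | pre-existing |
| negative or missing | positive | positive, ≥4-fold | treatment-emergent | treatment-boosted |
| negative or missing | positive | negative | none | pre-existing |
| positive | negative | positive, <4-fold | pre-existing | treatment-emergent |
| positive | negative | positive, ≥4-fold | treatment-boosted | treatment-emergent |
| positive | negative | negative | pre-existing | none |

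The fold change is relative to whichever baseline is positive. The first two rows are false treatment-emergent cases; the fourth and fifth are missed ones. With a missing parent result, only the first three rows can arise, so that clause can add false treatment-emergent cases but cannot remove true ones.

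**4. Size of the false treatment-emergent group.** Count = n × p × s, where p is the share negative or missing at parent baseline but positive before first dose, and s is the share of those positive again after dosing. The documents give neither; p = 0.5% to 5% and s = 25% to 100% are assumptions.

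- n = 915, low end: 915 × 0.005 × 0.25 = 1.1.
- n = 915, middle: 915 × 0.02 × 0.50 = 9.2.
- n = 915, high end: 915 × 0.05 × 1.00 = 45.8.
- n = 689: 689 × 0.005 × 0.25 = 0.9, up to 689 × 0.05 × 1.00 = 34.5.

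The number of missed cases and the number of missing parent baselines cannot be sized from the documents.

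**The case against.** The parent baseline is a deliberate convention, applied alike to efficacy, safety, PK, ADA and pharmacodynamics. A second ADA baseline would put two definitions into the pooled All columns that SAP 2.3.2 requires. The by-visit ADA table would already show pre-dose positivity by category and parent study. The endpoint is secondary and descriptive, with no test or decision rule, and the size rests on assumed rates.

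The points on size and standing are sound and limit how much weight this deserves. The uniformity point calls for a sensitivity summary under the current rule but does not defend the rule for this category. The by-visit table reveals pre-dose positives without reclassifying anyone.

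Three stronger readings are tempting, and the documents do not support them.

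- A reader might infer that treatment-emergent incidence is inflated overall. The reverse pattern (positive at parent baseline, negative before first dose, positive after) is undercounted, and nothing in the documents says which is commoner.
- A reader might infer that every pre-drug positive is counted as treatment-emergent. The rule also requires a negative or missing parent baseline and a further positive after dosing. Multiplying an assumed pre-dose rate by 915 therefore presumes full persistence and full roll-over.
- A reader might infer that planned ADA-safety, ADA-efficacy and ADA-PK tables are wrong. SAP 2.4.7.3 to 2.4.7.5 make those correlations optional, as does Protocol 11.4.4.2.

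**Conclusion.** The point holds as a two-way misclassification confined to the Placebo/Dupilumab category. As written, the plan ignores an analyzed pre-dose sample and judges ADA response against one taken nominally 12 weeks (PDY14192), 24 weeks (EFC13691), at least 40 weeks (DRI12544) or 52 weeks (EFC13579) before first dupilumab. The net direction is not established; only the missing-baseline clause has a known sign, and it adds false treatment-emergent cases.

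Under the stated assumptions, about 1 to 46 of at most 915 patients would be wrongly called treatment-emergent. Any ADA-impact exploration that is carried out would inherit the error. Nothing changes for the primary endpoint or the sample size. The change is still worth making, because the better comparator has already been collected and even a few wrong calls could matter if true incidence is low.

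**What to change.** For Placebo/Dupilumab patients, define ADA baseline in the pre-existing, treatment-emergent and treatment-boosted definitions as the last non-missing ADA result before the first LTS12551 dose. Use the parent baseline only if no such result exists.

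For DRI12544 patients, specify the later of the parent end-of-study sample and the LTS12551 Visit 1/2 sample. Pointing to Week 0 is not enough: SAP 2.1 and 2.5.4 take Week 0 from the DRI12544 end-of-study visit when available, even if a later LTS12551 sample exists.

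Keep the parent baseline for Dupilumab/Dupilumab. Report the current parent-baseline rule as a sensitivity summary, including for the pooled All columns, and document the departure from Protocol 11.4.4.2.

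The cost is SAP wording, one added derivation, one extra summary and the documented departure, with no new sampling. The downside is an ADA baseline that differs between the two treatment categories, which table footnotes should state.

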2.1.7 Pharmacodynamic/genomics endpoints

2.1.7.1 Whole blood biomarkers

Blood eosinophil count will be measured as part of the standard 5-part white blood cell (WBC) differential cell count on a hematology auto analyzer.

2.1.7.2 Serum biomarkers

Serum total IgE will be measured with a quantitative method (eg, ImmunoCAP) approved for diagnostic testing at Visit 1, Visit 13 (Week 48), Visit 16 (Week 84), and Visit 17 (End-of-Treatment).

Serum IgM, IgA, IgG and IgG subtypes will be measured with immunoassays at Visit 1, Visit 11 (Week 24), Visit 13 (Week 48), Visit 16 (Week 84), and Visit 17 (End-of-Treatment).

The collection for serum immunoglobulin and serum total IgE will be stopped after the approval of protocol amendment 4. The analyses for the total IgE in LTS12551 study will be restricted to the patients from DRI12544 study and performed to the data observed up to the end of collection.

2.2 DISPOSITION OF PATIENTS

This section describes patient disposition for both patient study status and the patient analysis populations for LTS12551 only, unless otherwise specified.

- Screened patients are defined as the patients who signed the informed consent.
- Enrolled patients are defined as the patients who signed the informed consent and had a treatment kit number allocated and recorded in the IVRS/IWRS database, regardless of whether the treatment kit was used.
- The safety population consists of the patients who actually received at least one dose or part of a dose of the LTS12551 study medication.

For patient study status, the total number of patients in each of the following categories will be presented in the clinical study report via using a summary table:

- Screened patients
- Screen failure patients and reasons for screen failure
- Non-enrolled but treated patients
- Enrolled patients (Overall and by parent study)
- Enrolled but not treated patients

Enrolled and treated patients (by the treatment category and overall, defined in Section 2.3.2)

- Patients who discontinued study treatment by main reason for permanent treatment discontinuation
- Status at last study contact

For all categories of patients (except for the screened and non-enrolled categories), percentages will be calculated using the total number of all enrolled patients as the denominator. Reasons for treatment discontinuation will be supplied in tables giving numbers and percentages. This summary will be provided by the treatment category (see Section 2.3.2) and may also by region/pooled countries.

A patient is considered as lost to follow-up at the end of study if he/she is not assessed at the last protocol planned visit.

All critical or major deviations potentially impacting safety evaluation, drug-dispensing irregularities, and other major or critical deviations will be summarized in tables giving numbers and percentages of deviations by treatment category.

Additionally, the analysis populations for safety, efficacy, PK and Anti-drug antibody will be summarized in a table by number of patients in the enrolled population.

- Safety population (for both safety and efficacy analyses)
- Pharmacokinetics population
- Anti-drug antibody population

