10.1.1.17 Visit 18 (End-of-Study: Month 27, Week 108)

End-of-Study (EOS) visit is scheduled 12 weeks after EOT.

- Record all medication use with start dose in e-CRF including starting dose.
- Inquire about AEs/SAEs and background asthma therapy tolerability.
- Measure vital signs (blood pressure, heart rate, respiration rate, body temperature, weight).
- Perform physical examination.
- Administer health care resource utilization questionnaire.
- Perform spirometry:
 - Spirometry will be performed after withholding the last dose of salbutamol/albuterol or levosalbutamol/levalbuterol for at least 6 hours and withholding the last dose of LABA for at least 12 hours (ultra-LABA like vilanterol should be withheld for at least 24 hours) and withholding the last dose of LAMA for at least 24 hours prior to administration of investigational product. This will be verified before performing the measurements.
- Perform 12-lead ECG.
- Perform blood sampling for:
 - Clinical laboratories.
 - Serum sample (predose) for PK and anti-dupilumab antibody analysis.
- Perform urine pregnancy test (for women of childbearing potential).
- Obtain urine for urinalysis (dipstick).
- Call IVRS/IWRS to register the EOS date.

10.1.2 For patients enrolled after Amendment 04

The visit schedule for patients enrolled after Amendment 04 are shown in the study flowchart in [Section 1.3](#).

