10.3.5 Procedure and consequence for patient withdrawal from study

The patients may withdraw from the study before study completion if they decide to do so, at any time and irrespective of the reason.

For patients who fail to return to the study site, the Investigator should make the best effort to re-contact the patient (eg, contacting patient's family or private physician, reviewing available registries or health care databases), and to determine his/her health status, including at least his/her vital status. Attempts to contact such patients must be documented in the patient's records (eg, times and dates of attempted telephone contact, receipt for sending a registered letter).

If possible, the patients are assessed using the procedures normally planned for the EOT Visit, including a PK sample, if appropriate.

A patient should only be designated as lost to follow-up if the site is unable to establish contact with the patient after 3 documented attempts via 2 different methods (phone, text, e-mail, certified letter, etc).

Patients who have withdrawn from the study cannot be re-enrolled (treated) in the study. Their inclusion and treatment numbers must not be reused. The statistical analysis plan (SAP) will specify how these patients lost to follow-up for their primary endpoints will be analyzed. The patients may withdraw from the study before study completion if they decide to do so, at any time and irrespective of the reason.

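### SAP 2.2 counts every patient without an end-of-study assessment as lost to follow-up, contrary to the contact-attempt rule in protocol 10.3.5

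*SAP*

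**What the plan says.** SAP Section 2.2 (Disposition of patients) lists the study-status categories to be tabulated. They include reasons for permanent treatment discontinuation and a row for status at last contact. After the list it adds: "A patient is considered as lost to follow-up at the end of study if he/she is not assessed at the last protocol planned visit."

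The last planned visit is Visit 18, at Week 108 for patients enrolled before Amendment 04 and Week 60 for those enrolled after it. Protocol 10.1.1.17 places it as follows: "End-of-Study (EOS) visit is scheduled 12 weeks after EOT". Protocol 10.1.2.13 has the same interval.

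Protocol Section 10.3.5 sets a different test: "A patient should only be designated as lost to follow-up if the site is unable to establish contact". Its threshold is that the site is "unable to establish contact with the patient after 3 documented attempts via 2 different methods". The same section treats withdrawal as a decision of the patient: "The patients may withdraw from the study before study completion if they decide to do so, at any time and irrespective of the reason". If someone stops attending, the site must try "to determine his/her health status, including at least his/her vital status". On the SAP's role it says: "The statistical analysis plan (SAP) will specify how these patients lost to follow-up for their primary endpoints will be analyzed."

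**The concern.** The two documents give the same label two meanings. The protocol's meaning is failure of contact. The SAP's meaning is absence of one visit assessment, whatever the reason.

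In a long-term safety study, a reader uses the lost-to-follow-up figure to judge how much safety information is unknown. Here the EOS visit closes the treatment-emergent window. Protocol 11.3.2 ends that window at the last dose plus 2 weeks plus 12 weeks, and EOS falls 2 + 12 = 14 weeks after the last dose. A missed EOS therefore does leave a gap, but it does not mean the patient's status is unknown. Protocol 10.1 requires monthly telephone contact for safety after Week 24, and 10.3.5 requires sites to pursue vital status. A figure that mixes unreachable patients with patients whose outcome is known does not tell the reader what it appears to. It can also disagree with site records kept under the protocol rule.

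**Working it through.** The documents state no lost-to-follow-up, death or withdrawal count, so there is no figure to reproduce. The check compares the two rules.

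**Step 1. Does anything reconcile them?**
- SAP 1.6 says this SAP version is based on amended protocol 2, so an older protocol does not explain the difference.
- SAP 1.5 and 1.6 list changes from the protocol and from earlier SAP versions. A new definition of lost to follow-up is not among them.
- Protocol 10.3.5 leaves to the SAP how lost patients are analysed. It does not leave to the SAP who they are.
- SAP 2.5.3 (Missing data) does not mention these patients. The sentence in 2.2 is the only definition I found in the SAP.

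**Step 2. Apply both rules to each type of patient.**

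| Patient | SAP 2.2 | Protocol 10.3.5 |
|---|---|---|
| (a) Died before EOS, death known to the site | Lost | Not lost |
| (b) Withdrew from the study before EOS, status known | Lost | Not lost |
| (c) Reached, for example by telephone, but not assessed at EOS | Lost | Not lost |
| (d) Not reached after three attempts by two methods | Lost | Lost |
| (e) Stopped study drug early but attended EOS | Not lost | Not lost |

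**Step 3. Direction.** The rules disagree in (a), (b) and (c), and each time the SAP adds a patient. Group (d) is lost under both. So

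SAP count − protocol count = n(a) + n(b) + n(c) ≥ 0.

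**Step 4. Size.** The documents give none of n(a), n(b) or n(c). Only a scale can be stated. SAP 2.2 takes disposition percentages over all enrolled patients, so each 1% of enrolled patients in groups (a) to (c) adds one percentage point to the lost figure. That is 0.01 × 2930 ≈ 29 patients at the SAP 1.3 maximum (776 + 1902 + 210 + 42 = 2930), or 0.01 × 2206 ≈ 22 at the protocol synopsis's expected enrolment. The 1% is a unit for scaling, not an estimate.

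**Step 5. What the label feeds.** The primary endpoint is the number and percentage of patients with any treatment-emergent adverse event, over the safety population (protocol 11.4.3.1.1; SAP 2.4.5.1). The label enters neither numerator nor denominator. As written, it also enters no exposure, event-rate, Kaplan-Meier or efficacy summary.

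**The case against.** The strongest reply is that the sentence may do little. Lost to follow-up is not one of the listed rows in SAP 2.2, and no table is tied to the sentence. The row for status at last contact might show deaths and known statuses separately. The words about the end of the study suggest the author may have meant a completion flag rather than a rival definition. Part of this stands: the SAP specifies no particular table with an inflated count. It does not remove the conflict. The categories of the status row are undefined, the sentence is explicit, and a programmer following it would produce the wrong classification. If a completion flag was meant, it has the wrong name.

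The reply also has force against three stronger readings that a reader might infer.

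- *Deaths are hidden among unknown outcomes.* They are not. SAP 2.4.5.2 tabulates and lists deaths, and the adverse event overview in 2.4.5.1 counts events leading to death. A death could be labelled lost in disposition and still be correctly reported elsewhere.
- *Everyone who stops treatment becomes lost.* Protocol 10.3.2 and 10.3.4 keep such patients in follow-up through EOS. Those who attend are not caught. Only withdrawal from the study before EOS is.
- *The count is inflated several-fold.* Any such multiple would come entirely from assumed rates of missed visits and true loss. The documents supply neither.

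**Conclusion.** SAP 2.2 contradicts protocol 10.3.5 and is wrong as written. Read literally, it mislabels as lost to follow-up the patients who died, withdrew from the study before EOS, or were reached but not seen at EOS. The lost count can only be overstated, by an amount the documents do not allow to be computed.

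The conclusion rests on two readings: that the protocol's restrictive wording makes its contact rule exclusive, and that the SAP sentence will be applied as it stands.

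The consequence is limited to disposition reporting. A reader might infer that the primary safety result is biased. The documents do not support that, because the label plays no part in that analysis.

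**What to change.** Replace the SAP 2.2 sentence with the definition in protocol 10.3.5, by cross-reference. Add a separate disposition line, *last planned visit not performed*, split into death, withdrawal from the study, lost to follow-up per protocol, and other. This keeps the missed-visit information under an accurate name.

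The text change is small and needs no new patient assessment. The remaining cost is a data check. Protocol 10.3.5 requires contact attempts to be documented in the patient's records, and neither document shows an e-CRF field for contact-attempt status or for the reason EOS was missed. The sponsor should confirm where both are captured before the table is specified. If they are held only in site records, they will have to be retrieved from there.
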